#### **4.2.4 Incomplete dates for the last administration of LCM**

For purposes of imputing missing components of partially reported dates for the last administration of LCM, the algorithms listed below will be followed. Stop dates of LCM will be displayed as reported in the subject data listings (ie, no imputed values will be displayed in data listing).

- Missing last administration day, but month and year present:

The last administration day will be set to the last day of the month or the date of the final contact, whichever is earlier in the month.

- Missing last administration day and month, but year present:

The last administration day will be set to the last day of the year or the date of the final contact, whichever is earlier in the year.

- Completely missing date of last administration:

The last administration date will be imputed for the duration of exposure only as the date of last contact according to the study termination form. A review of the data will be performed to ensure that the imputation does not result in an unrealistic value for duration of exposure.

If a subject died during the study, and the imputed last administration date according to the rules above is after the date of death, the last administration date will be assigned to the date of death.

#### **4.3 Interim analyses and data monitoring**

No formal interim analysis is planned for this study; however, data will be presented to and reviewed by a DMC. The objectives and procedures for the DMC will be detailed in the DMC Charter.

#### **4.4 Multicenter studies**

Unless otherwise stated, descriptive summaries for individual sites will not be presented. Subject data listings will provide data grouped by site.

#### **4.5 Multiple comparisons/multiplicity**

There will be no adjustment for multiplicity in this study.

#### **4.6 Use of an efficacy subset of subjects**

Not applicable.

#### **4.7 Active-control studies intended to show equivalence**

Not applicable

#### **4.8 Examination of subgroups**

If not stated otherwise, summaries will be presented by age groups as given in [Section 3.2.5](#).

Separate age subgroupings are used for the purpose of summaries of questionnaires with different versions according to the age of the subject. Details are described in the corresponding sections describing the analysis of the questionnaires.

The following syndrome subgroups will be used to investigate AEs and seizure days:

- Infantile spasms/West syndrome
- Lennox Gastaut syndrome
- Dravet Syndrome
- Other symptomatic generalized epilepsy
- Primary generalized epilepsy

The classification of subjects to the syndromes will be done by a medical review and agreed during the DEM. Only subgroups with at least 4 subjects will be presented.

For the presentation of summaries by syndrome subgroups, the syndrome subgroups will be used instead of the age groups, ie, summaries will not be presented by syndrome and age group.

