5.4 Rationale for study design and selection of dose

Epilepsy is a condition for which an improved benefit/risk ratio for medicinal products remains a challenge; this is especially true for pediatric patients. Based on the demonstrated efficacy and safety of LCM as adjunctive treatment in adult subjects with partial-onset seizures, and the experience with other AEDs in pediatric subjects, it is expected that LCM will also exhibit an acceptable benefit/risk profile in the pediatric population with uncontrolled generalized seizures.

In this study, the safety and tolerability of LCM will be studied when added to 1 to 3 concomitant AEDs in pediatric subjects with epilepsy syndromes associated with generalized seizures. The study will also obtain preliminary efficacy data of LCM on seizure frequency in pediatric epilepsy syndromes associated with generalized seizures.

This study is an exploratory study to investigate on which syndromes LCM has a beneficial effect in order to plan confirmatory study(ies) and exclude syndromes for which LCM has no clear benefit or possibly induces exacerbations.

Based on the currently available LCM pediatric safety and PK data from SP847 and SP1047, as well as on information available in the medical literature, the dosing recommendations for SP0966 are as follows:

- Lacosamide dosing should aim to achieve LCM plasma concentrations equivalent to the average steady-state LCM plasma concentration reached after a LCM 200 to 600mg/day dose administration in adult studies.
- A weight-based flexible dosing scheme is recommended:
 - Subjects <50kg: LCM 4-12mg/kg/day (oral solution)
 - Subjects ≥50kg: LCM 200 to 600mg/day (tablets/oral solution)

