6 SELECTION AND WITHDRAWAL OF SUBJECTS

6.1 Inclusion criteria

To be eligible to participate in this study, all of the following criteria must be met:

1. A signed informed consent has been obtained from the parent/legal representative and assent has been obtained from the subject (when possible or as required according to local Institutional Review Boards [IRBs]/Independent Ethics Committees [IECs]).
2. Subject and/or caregiver (which may be a parent, a legal representative, or other caregiver) are willing and able to comply with all study requirements including maintaining a daily seizure diary.
3. Subject is male or female, ≥1 month to <18 years of age. For preterm infants <1 year old, the corrected gestational age should be used when determining eligibility. The generally accepted definition of corrected gestational age, which is calculated by subtracting the number of weeks born before 37 weeks of gestation from the chronological age, will be used for this study.

4. Subject has a diagnosis of uncontrolled epilepsy with generalized seizures (Type II) according to the International Classification of Epileptic Seizures (1981) (see Section 17.1). The underlying epilepsy syndrome should be documented. Diagnosis should have been established by clinical history and an EEG with generalized spike-wave discharges. Documentation of the EEG finding of generalized spike waves (EEG recording or a report) is required. The EEG should have been performed no more than 18 months prior to Visit 1 (with no change to diagnosis or seizure types during this time).
5. Subject must have experienced 2 or more events (typical generalized seizures associated with diagnosed epilepsy syndrome) within the 6-week prospective Baseline Period.
6. Subject is on a stable dosage regimen of 1 to 3 AEDs. The daily dosage regimen of concomitant AED therapy must be kept constant for a period of at least 4 weeks prior to the Baseline Period.
7. Vagal nerve stimulation is allowed and will not be counted as a concomitant AED. The VNS device must be implanted for at least 6 months before Visit 1 and the device settings must be stable for at least 4 weeks before Visit 1 and be kept stable during the Baseline Period and the Treatment Period. Use of the VNS device magnet is allowed.
8. Body weight at Visit 1 is at least 4kg for infants.
9. Females of childbearing potential must have a negative pregnancy test at Visit 1.

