7.9 Blinding

SP0966 is an open-label study; thus, there will be no blinding.

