### 3.4 Protocol deviations

Important protocol deviations are deviations from the protocol which could potentially have a meaningful impact on the primary or secondary safety outcomes or preliminary efficacy outcomes for an individual subject. The criteria for identifying important protocol deviations and the classification of important protocol deviations will be defined separately in the Specification of Protocol Deviations (SPD) document. To the extent feasible, rules for identifying protocol deviations will be defined without review of the data and without consideration of the frequency of occurrence of such deviations. Whenever possible, criteria for identifying important protocol deviations will be implemented algorithmically to ensure consistency in the classification of important protocol deviations across all subjects.

Important protocol deviations will be reviewed as part of the Data Evaluation Meeting (DEM) prior to database lock.

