### 8.3 Exploratory safety variables

A frequency table will be presented for the number of subjects with a decrease of at least 30% and a decrease of at least 50% in generalized spike-wave discharges on 24-hour EEG at Visit 6 compared to Baseline by syndrome subgroups

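### Syndrome groups are not tied to baseline information, and spike-wave increases are not tabulated by syndrome although decreases are

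*SAP*

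**What the plan says.** - **Purpose.** Protocol 5.4 says the study is meant to show where the drug helps, so that confirmatory studies can be planned, and to "exclude syndromes for which LCM has no clear benefit or possibly induces exacerbations".
- **Entry record.** Inclusion criterion 4 (Protocol 6.1) states: "The underlying epilepsy syndrome should be documented".
- **Assignment to groups.** SAP 4.8 names five groups, including a residual category for other symptomatic generalized epilepsy. It then says: "The classification of subjects to the syndromes will be done by a medical review and agreed during the DEM". It gives no classification rule, source data, cut-off visit or restriction on what reviewers may see.
- **Timing and blinding.** SAP 3.4 places the meeting before lock: "Important protocol deviations will be reviewed as part of the Data Evaluation Meeting (DEM) prior to database lock". Protocol 7.9 states: "SP0966 is an open-label study; thus, there will be no blinding".
- **Display rule.** SAP 4.8: "Only subgroups with at least 4 subjects will be presented".
- **EEG by syndrome.** SAP 8.3 tabulates the "number of subjects with a decrease of at least 30% and a decrease of at least 50% in generalized spike-wave discharges" at Visit 6, by syndrome.
- **EEG increases.** SAP 8.1.1 tabulates rises of at least 30% and at least 50% at Visit 6 and mentions no syndrome split. Under the default in SAP 3.1 the table is shown overall and by age group.

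**The concern.** There are two separate gaps, and both bear on the syndrome comparison that Protocol 5.4 presents as the reason for the study.

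First, syndrome is a baseline characteristic, yet the SAP settles it at a meeting held shortly before lock, when diary and EEG results will largely have been collected. Judgement calls are foreseeable: there is a residual category, and subjects with mixed Type I and Type II seizures are eligible. If a reviewer knows how a borderline subject fared, that knowledge can affect the group chosen. SAP 3.4 guards against this kind of influence for protocol deviations, asking that rules be set as far as feasible without looking at the data and be applied by algorithm. SAP 4.8 has no equivalent safeguard. Disposition, demographics, seizure days, adverse events, hospital use and responder rates are all repeated by syndrome, so one classification affects them all.

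Second, a syndrome in which discharges rise in some subjects and fall in others would have only its falls counted by syndrome. For a variable listed under safety, in a study meant to detect exacerbation, the tabulated direction is the less informative one.

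**Working it through.** The plan has no figure of its own to reproduce here: SAP 2.4 says that no formal sample size calculation was done, and no number depends on the classification. The check compares passages and then works out how much one subject can matter.

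**1. Is the syndrome split for EEG increases implied?** Where the SAP wants a syndrome repeat it says so: 5.1 (disposition), 6.1 (demographics), 8.1.2 (seizure days), 8.2.2 (adverse events), 9.1.5 (hospital and emergency use) and 9.2 (responders and worsening). SAP 8.1.1 says nothing, so the SAP 3.1 default applies. SAP 4.8 itself names only adverse events and seizure days as uses of the syndrome groups. The split is therefore absent, for the increase table and also for the descriptive summary of EEG values and changes.

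**2. Which measures of worsening are shown by syndrome?** Change in generalized seizure days, in both directions (SAP 8.1.2); the proportion with more than 30% and 50% increase in generalized seizures (SAP 9.2); and treatment-emergent adverse events (SAP 8.2.2). Spike-wave increases are missing.

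**3. Largest effect of moving one subject.** Let a group have x events in n, and let the moved subject have outcome y (0 or 1).
- Moving in: (x+y)/(n+1) − x/n, at most 1/(n+1) in size.
- Moving out: (x−y)/(n−1) − x/n, at most 1/n in size.

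| Move | Extreme case | Shift |
|---|---|---|
| Into a group of 4 | 0/4 to 1/5 | 20 points |
| Out of a group of 5 | 1/5 to 0/4 | 20 points |
| Into a group of 10 | 0/10 to 1/11 | 9.1 points |
| Out of a group of 10 | 1/10 to 0/9 | 10 points |

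These are maxima. Less extreme cases move less: 2/5 to 2/4 is 10 points, and 1/4 to 2/5 is 15. Moving one subject out of a group of 4 leaves 3, and the display rule then removes that syndrome from the tables. An average of 50/5 = 10 per group assumes equal groups, which the documents do not state.

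**4. Bias if a move depends on outcome (illustration).** Assume two syndromes share a true response rate p, and one non-responder is moved from a group of n+1 to a group of n. Ignoring the rare case in which everyone responds, the expected false gap is (n+1)p/n − np/(n+1) = p(2n+1)/[n(n+1)].
- Groups of 5 and 4 (n=4): 0.45p, which is 4.5 points at p=10% and 13.5 at p=30%.
- Groups of 11 and 10 (n=10): 0.191p, which is 1.9 points at p=10% and 5.7 at p=30%.

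A simulation at p=30% that allows for the rare case gave about 13 and 6 points. With classification blind to outcome, the expected gap is zero. The response rates are assumptions.

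**5. How often would an EEG increase go untabulated by syndrome?** If a proportion q of subjects has a rise of at least 30%, the chance that a syndrome contains at least one is 1 − (1−q)^n. For q from 10% to 30% (assumed), this is 34% to 76% at n=4 and 65% to 97% at n=10.

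**The case against.** The strongest reply is that neither document says reviewers will see outcomes by subject. SAP 4.8 does not say when the medical review starts, and Protocol 13.5 describes the pre-lock data cleaning meetings as blinded. The syndrome should be on record at entry, diagnosis and seizure types should not have changed since the qualifying EEG, and West syndrome requires hypsarrhythmia on the Baseline EEG, so the room for reassignment is limited. Clinical worsening is visible by syndrome through seizure days, seizure increases, adverse events and reasons for discontinuation. Each subject's EEG change will be in the listings that SAP 3.1 requires. All analyses are descriptive, and no formal decision rule exists.

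Most of this stands, and it rules out some stronger readings. A reader might infer that groups will be assigned with results in view; the text supports only that nothing prevents it. The word blinded in Protocol 13.5 does not close that gap, because there is no treatment blind to keep and SAP 3.4 does not repeat the word. A reader might infer that syndrome reporting can show only benefit; that is wrong outside the EEG. A reader might also put the effect of one move at 1/4 = 25 points. That is the effect of changing one outcome in a group of 4. As a move it would require going from 4 to 3, and a group of 3 is not displayed.

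The reply does not explain why SAP 4.8 leaves the classification unconnected to the entry record, or why decreases are tabulated by syndrome and increases are not. Listings are no substitute for a count by syndrome set beside the decreases.

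**Conclusion.** The point holds as two modest and separate gaps. The syndrome classification is not bound to baseline information, so outcome-dependent assignment is possible, though not stated or shown. And EEG aggravation is not tabulated by syndrome, although EEG improvement is. The first gap touches every syndrome table; the second is confined to generalized spike-wave discharges.

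One move can shift a displayed rate by at most 20 points in a group of 4 or 5 and by 9 to 10 points near 10 subjects, or remove a group of 4 from display. These limits are arithmetic and need no assumption beyond group size; the expected-gap and untabulated-increase figures rest on assumed rates. Because the analyses are descriptive, the risk is to interpretation and not to an error rate. It still matters, because these descriptive results are what Protocol 5.4 intends to use in choosing syndromes for confirmatory study. The change is worth making mainly because it costs so little.

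**What to change.** **SAP 4.8.** State that the classification uses Visit 1-2 information only: the syndrome documented at entry, the history and the baseline EEG. Have the reviewers already planned do it without access to post-Visit 2 data, and finalise it before the Data Evaluation Meeting. List every subject whose group departs from the entry diagnosis, with the reason.

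**SAP 8.3 (and the matching entry in 2.2.1.4).** Tabulate rises of at least 30% and at least 50% in generalized spike-wave discharges at Visit 6 by syndrome, beside the falls. Exact confidence intervals would help readers of small groups but are optional.

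**Cost.** Some SAP wording, earlier timing for a review that is already planned, and one extra table. No study procedure changes.

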### **5 STUDY POPULATION CHARACTERISTICS**

#### **5.1 Subject disposition**

The number of subjects screened, and the number and percentage of those subjects who were screen failures, broken down by primary reason for screening failure, will be presented for all subjects screened.

An overall summary of disposition for the SS will present the number and percentage of subjects completing the study and subjects discontinuing along with the reason for discontinuation. This summary will be presented overall as well as for the Titration Period and the Maintenance Period. The disposition summary will be repeated by syndrome subgroups (as described in [Section 4.8](#)).

The number and percentage of subjects who discontinued due to AEs broken down by type of AE will be presented overall only (ie, not by age group). The type of AE will be derived by combining outcome (fatal or not) and seriousness (serious or not) of all these AEs (for several AEs, if applicable) as given in the UCB Standard TFL Shells (see Table DS T 04).

The date of first subject in, date of last subject out, number of screened subjects, and the number of subjects in each analysis set (SS, FAS, and PK-PPS) will be summarized overall and by site for all subjects screened. Subjects who transferred sites will be summarized according to their original site. The summary by site will not be presented by age groups.

Additionally, the number and percentage of subjects in the different analysis sets (SS, FAS, and PK-PPS) will be provided.

## 5.2 Protocol deviations

Important protocol deviations defined in the SPD, and additionally identified at the DEM before database lock, will be listed for the SS.

The number and percentage of subjects with at least 1 important protocol deviation will be summarized overall and by category of important protocol deviation for the SS. The number and percentage of subjects with no important protocol deviations will also be presented in this summary. This summary will not be presented by age group.

## 6 DEMOGRAPHICS AND OTHER BASELINE CHARACTERISTICS

### 6.1 Demographics

The BMI will be calculated using the formula

$$\text{BMI} = \text{weight (kg)} / (\text{height (m)})^2.$$

The following demographics will be summarized for the SS:

- Age (years) – continuous and categorized as (28 days - <24 months, 24 months - <12 years, 12 years - <18 years)
- Gender (male, female)
- Race (American Indian/Alaskan Native, Asian, Black, Native Hawaiian or Other Pacific Islander, White, Other/Mixed)
- Ethnicity (Hispanic or Latino, not Hispanic or Latino)
- Height (cm)
- Weight (kg)
- BMI (kg/m^2)
- Head circumference (cm)

The demographics summary will be repeated by syndrome subgroups (as described in Section 4.8).

### 6.2 Other Baseline characteristics

The time since first diagnosis will be given in years (with 2 decimal places) and will be derived with the following formula:

$$(\text{Date of informed consent} - \text{date of diagnosis}) / 365.25$$

Partial dates will be imputed. If the month and year are available, the diagnosis date is imputed as the later of the following dates: the first day of the month, the subject's birthdate, or the date of the first seizure (if available). If only a year is available, the later of the following dates will be imputed: January 1st of the year, the subject's birthdate, and the date of the first seizure. Completely missing dates will not be replaced and the time since first diagnosis will be set to missing.

The age at first diagnosis will be derived using the same formula as age (see [Section 3.2.5](#)) but using the date of first diagnosis of disease instead of the date of informed consent. Partial dates of first diagnosis will be completed as described for the time since diagnosis. If the date of birth is incomplete, the age at first diagnosis will be derived as follows:

- For subject with a partial date of birth with available information about year and month, use the first day of the month to impute the date of birth and use the imputed date of birth to calculate age at first diagnosis.
- For subject with a partial date of birth with available information about year only, use age as given in the eCRF and subtract the time between (imputed) date of diagnosis and informed consent (ie, [date of informed consent – date of diagnosis] / 365.25).

Completely missing dates will not be replaced and the age at first diagnosis will be set to missing.

Antiepileptic drugs will be defined as medications documented on the “Concomitant Medications (AEDs only)” log form. A medical review will be performed to ensure that the medications are documented correctly. Corrective measurements (correction of documentation or programmatic mapping to the correct medication category [AED or not]) will be applied as applicable. Concomitant AEDs at Baseline will be defined as all concomitant AEDs given on the date of first dose of LCM. Medications will be counted only once per unique WHO-DD preferred name.

The following Baseline characteristics will be summarized for the SS:

- Time since first diagnosis (years)
- Age at diagnosis (years)
- History of withdrawal seizures (yes, no)
- History of status epilepticus (yes, no)
- Number of concomitant AEDs at Baseline (1, 2, 3)

The ILAE Seizure classification (1981) history for the last 12 months will be summarized for the SS presenting number and percentage of subjects with the following categories:

- Partial-onset seizures
  - Simple partial with motor signs (I A1)
  - Simple partial with somatosensory or special sensory symptoms (I A2)
  - Simple partial with autonomic symptoms or signs (I A3)
  - Simple partial with psychic symptoms (I A4)

- 
- Complex partial (I B)
  - Partial evolving to secondarily generalized (I C)
  - Generalized seizures
    - Absence (II A)
    - Myoclonic (II B)
    - Clonic (II C)
    - Tonic (II D)
    - Tonic-clonic (II E)
    - Atonic (II F)
  - Unclassified epileptic seizures
    - Unclassified epileptic seizures (III)

The historical seizure count form of the electronic Case Report form (eCRF) records the number of seizures per pre-selected ILAE seizure code experienced by the subject during the 4 weeks prior to the start of the study. These data will be provided in a subject data listing.

A listing of reproductive potential and birth control measures for female subjects will be provided.

### **6.3 Medical history and concomitant diseases**

The number and percentage of subjects with a medical history condition, including both resolved and ongoing conditions at the time of study entry, will be summarized overall and by MedDRA® primary system organ class (SOC) and preferred term (PT) for the SS.

